4.2.7 Mixed Model of Repeated Measures (MMRM)

As one of the sensitivity analyses, the mixed model of repeated measures (MMRM) will be used. Longitudinal models with correlated errors, otherwise widely known as MMRMs, have been increasingly used for the analysis of clinical trials with missing data. A longitudinal model is often used even though the primary objective is to estimate a treatment effect and test a null hypothesis of no treatment effect at a single specific time-point (typically at the end of double-blind period). The advantage of using an MMRM analysis in this context (compared to ANCOVA at the primary time-point) is that longitudinal models include all randomized subjects regardless of whether they completed the study (provided data for the primary time-point) or not. Model estimation and inference is done without performing any imputation of the missing data for subjects who discontinued early, yet partial data available for these subjects is fully utilized and contributes to the estimation of effects and to the variance-covariance structure of the longitudinal model.

The MMRM can contain terms for baseline measurement, treatment arm, visit, treatment by visit interaction, and the stratification variables. Details will be given case-by-case for each endpoint. The least squares mean estimates of change from baseline for each treatment group and their difference, and associated 95% CI will be provided. Due to the large amount of visits to include in the model, the unstructured covariance pattern model will be selected first. If the algorithm for unstructured covariance pattern does not converge, then the heterogeneous Toeplitz structure will be used instead. If this second model also does not converge, then the (homogeneous) Toeplitz structure will be selected, thereafter the compound symmetry and finally the first order autoregressive covariance structure will be used to achieve convergence.

4.2.8 Pattern Mixture Models

To address the possibility of the Hb data being missing not at random (MNAR), Pattern Mixture Models (PMM) will be implemented as sensitivity analyses. Pattern Mixture Models (PMM) provide a general and flexible framework for sensitivity analyses that allows formulating assumptions regarding missing data in a transparent and clinically interpretable manner. A variety of PMMs with different types of MNAR assumptions will be implemented.

4.2.8.1 PMM –Last Mean Carried Forward

A pattern-mixture model using a last mean carried forward multiple imputation method (Carpenter et al, 2013) will be used as another sensitivity analysis to explore the robustness of the ANCOVA results for the primary efficacy variables. Using this method, missing data after ending Week will be imputed based on the last non-missing mean from its own treatment group.

The steps to implement this sensitivity method is the same as for the multiple imputation ANCOVA method described in Section 4.2.6 with the exception of step 2, where the monotone datasets are imputed. The procedure for that is as follows. Parameters below refer to the parameters of the multivariate normal distribution for baseline and post baseline Hb measurement.

1. Create posterior distribution of parameters: Separately for each treatment group, take all subjects observed data and assuming MAR to fit a multivariate normal distribution with unstructured mean (i.e. a separate mean for each of the baseline plus post-baseline scheduled weeks and unstructured variance covariance matrix using a Bayesian approach with an improper prior for the mean and an uninformative Jereys' prior for the variance-covariance matrix (Schafer, 1997, p. 155).
2. Draw parameters: Separately for each treatment group, draw variance-covariance matrix from the posterior distribution for the parameters using seed 453628. The mean Vector would be set to the marginal mean for their randomized treatment arm at their last non-missing measurement.
3. Build joint distribution of missing data and observed data: For each subject with missing data, using the draws for the parameter to build the joint distribution of their observed and missing data.
4. Construct conditional distribution of missing data give observed data: For each subject with missing data, use their joint distribution in previous step to construct their conditional distribution of missing given observed outcome data. Sample their missing data from this conditional distribution, to create a “completed” data set, using seed 732545.

Repeat the above steps for 200 times and resulting in 200 fully imputed data sets. Then fit an ANCOVA model for each imputation data set, and combine the resulting parameter estimates and standard errors using Rubin’s rules (Rubin, 1987) for final inference.

4.2.8.2 PMM –Baseline Carried Forward (roxadustat only and both groups)

The analysis is similar to PMM – Last Mean Carried Forward, with a different assumption in imputing the missing data. The imputation data will be generated similarly as last mean carried forward method described above but instead of using post-baseline observed data, only baseline data will be used. The similar analyses will be conducted in two scenarios.

- The baseline carried forward imputation will be performed for the roxadustat treatment group only, while for active control group, the imputation data will be generated using the last mean carried forward described above.
- The baseline carried forward imputation will be performed for both treatment groups.

Similarly, the Rubin’s method will be then used to combine the estimates and the differences between the least square mean differences between the two treatment groups from each of the ANCOVA analysis.

4.3 Statistical Analyses

4.3.1 CV safety endpoints analyses

The CV safety evaluation strategy is to conduct pooled analyses of adjudicated data across the study program to ensure that the overall number of events is high enough to provide adequate power. Thus, all analyses of CV safety will be conducted in accordance with the PSAP.

4.3.2 Primary efficacy endpoint analysis for US

Mean change in Hb from baseline to the subjects mean level from week 28 to week 52 will be analyzed with multiple imputation ANCOVA as described in Section 4.2.5 and 4.2.6. The model will contain terms for the baseline Hb measurement, treatment arm, CV history, geographic region and dialysis duration. Non-inferiority of roxadustat compared to epoetin alfa will be declared, and this test is successful, if the lower bound of the 2-sided 95% confidence interval of the difference between roxadustat and epoetin alfa exceeds -0.75 g/dL. The ITT analysis set will be used.

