3.1 Inclusion criteria

For inclusion in the study subjects should fulfil the following criteria:

1. Provision of Informed Consent prior to any study specific procedures
2. Age \geq 18 years at screening visit 1
3. **Previous versions of the protocol prior to US amendment ver 6.0 and outside of US amendment ver 7.0:**
Receiving or initiating hemodialysis or peritoneal dialysis for treatment of native kidney end-stage renal disease (ESRD) at least 30 days prior to visit 1. Patients treated with hemodialysis must have access consisting of an arteriovenous fistula, AV graft, or tunneled (permanent) catheter. Patients on peritoneal dialysis must have a functioning peritoneal dialysis catheter in place.

Starting with US amendment ver. 6.0 and outside of US amendment ver 7.0 (changed to recruit incident dialysis patients only):

Receiving or initiating hemodialysis or peritoneal dialysis for treatment of native kidney end-stage renal disease (ESRD) for a minimum of 2 weeks and a maximum of 4 months prior to randomization. Patients treated with hemodialysis must have access consisting of an arteriovenous fistula, AV graft, or tunneled (permanent) catheter. Patients on peritoneal dialysis must have a functioning peritoneal dialysis catheter in place.

4. Two central laboratory Hb values during the screening period, obtained at least 7 days apart, must be <12 g/dL in patients currently treated with an erythropoietin analogue or <10 g/dL in patients not currently treated with an erythropoietin analogue. Patients are considered not currently treated if they have not received either Mircera® for at least 8 weeks or any other erythropoietin analogue for at least 4 weeks prior to visit 1.
5. Ferritin \geq 100 ng/mL at randomization (obtained from screening visit)
6. TSAT \geq 20% at randomization (obtained from screening visit)
7. Serum folate level \geq lower limit of normal (LLN) at randomization (obtained from screening visit)
8. Serum vitamin B12 level \geq LLN at randomization (obtained from screening visit)
9. Alanine aminotransferase (ALT) and aspartate aminotransferase (AST) \leq 3x upper limit of normal (ULN), and total bilirubin (Tbili) \leq 1.5 x ULN at randomization (obtained from screening visit)
10. Body weight 45 to 160 kg (prescribed dry weight)

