7.2.3.2 Patients not treated with erythropoietin analogue at study entry

The initial roxadustat dose (administered TIW) is based on a tiered, weight-based dosing scheme (Table 5). For example, a patient that has a dry weight of 80 kg would initiate roxadustat treatment with 100 mg orally TIW.

Table 5 Initial dosing of roxadustat dose for patients not taking erythropoietin analogue at study entry

Dry Weight (kg)	Roxadustat dose, mg TIW
45-70	70
>70-160	100

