1.3 Number of subjects

Primary efficacy variable: With at least 600 subjects, the study will provide at least 99% power to demonstrate non-inferiority of roxadustat versus epoetin alfa for the primary efficacy endpoint (i.e., Hb change from baseline to the average level during the evaluation period defined as Week 28 until Week 52). This assumes a difference (roxadustat minus epoetin alfa) of -0.30 g/dL, a non-inferiority margin for this difference of -0.75 g/dL and a standard deviation of 1.25 g/dL.

To contribute adjudicated CV events for the pooled CV analyses across the phase 3 program: approximately 2000 subjects will be randomized in a 1:1 ratio to either roxadustat or active control, i.e. epoetin alfa. The sample size for this study is driven by the overall requirement of adjudicated CV events for the phase 3 program in dialysis-treated CKD subjects (which consists of four studies in total targeting 611 subjects with MACE events). The three other studies in the study program are FG-4592-064, 1517-CL-0613, FG-4592-063.

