4.3.7 Subgroup analyses

Subgroup analysis will be performed for both the primary efficacy endpoints of Hb, with the ITT analysis set for the primary endpoint for US and the PPS for the primary endpoint for EU.

- Age: <65 and ≥ 65 ; <75 and ≥ 75 years
- Gender: Male vs Female
- Race: White, Black or African American, Asian, Native Hawaiian or other Pacific Islander, American Indian or Alaska native, other
- Weight: <70 kg vs ≥ 70 kg; and <100 kg vs ≥ 100 kg
- Weight by gender-specific median (4 groups)
- Body mass index (BMI): <30 and ≥ 30 kg/m²
- Geographical region: US vs Ex-US
- Geographical region:
 - North America
 - South America
 - Asia and Australia
 - Europe
- Peritoneal dialysis vs. Hemodialysis

- Cardiovascular/cerebrovascular/thromboembolic history: Yes or No
- Baseline Hb value: $\leq 10.5\text{g/dL}$ and $>10.5\text{g/dL}$
- Incident vs stable dialysis: dialysis duration ≤ 4 months vs >4 months from the randomization date
- Diabetes history: Yes vs No
- Epoetin alfa dose prior to randomization: $\leq 12,500$ IU/week and $>12,500$ IU/week
- Baseline hsCRP (\leq ULN vs $>$ ULN).

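### ESA treatment at entry is missing from the confirmatory, sensitivity and imputation models for Hb and from the primary-endpoint subgroups; only exploratory analyses isolate an ESA-naive or near-naive subset

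*SAP*

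**What the plan says.** ESA treatment at entry matters twice in the protocol.

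- **Eligibility.** Under Protocol 3.1, criterion 4, two central screening Hb values "must be <12 g/dL in patients currently treated with an erythropoietin analogue or <10 g/dL in patients not currently treated with an erythropoietin analogue". Not treated means no Mircera for 8 weeks, or no other analogue for 4 weeks, before visit 1.
- **Starting dose.** A treated subject randomized to roxadustat starts from a conversion table (7.2.3.1, Table 4). For an untreated subject, "The initial roxadustat dose (administered TIW) is based on a tiered, weight-based dosing scheme" (7.2.3.2). In the epoetin arm, treated subjects start from their current or converted dose (7.2.4.1, 7.2.4.2) and untreated subjects from a weight-based dose (7.2.4.3).

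Randomization is stratified by country only (Protocol 7.2.1, SAP 1.2.3).

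For the US primary endpoint, SAP 4.3.2 states: "The model will contain terms for the baseline Hb measurement, treatment arm, CV history, geographic region and dialysis duration". The imputation model (4.2.6), the EU primary MMRM (4.3.3), the other secondary Hb models (4.3.4) and the sensitivity analyses (4.3.6) use the same baseline factors. None has an ESA term.

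The SAP 4.3.7 subgroups for both primary Hb endpoints contain one ESA item, "Epoetin alfa dose prior to randomization", cut at 12,500 IU/week.

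Prior ESA use does appear in SAP 3.1.6.1 and 4.3.5.1. Time to target Hb, median time to target and Hb response by week 24 are analysed in anemic subjects who were ESA-naive or near-naive, meaning no ESA in the 4 weeks before randomization.

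**The concern.** The trial combines two clinical situations: converting a patient already on an ESA, and correcting anemia in a patient not on one. The protocol itself reads the same Hb differently in the two. A treated subject with mean screening Hb below 10 g/dL starts one dose step higher (7.2.3.1), while an untreated subject, who must screen below 10 g/dL, has no such step (7.2.3.2). So ESA status may well predict Hb at weeks 28-52 beyond baseline Hb.

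Leaving it out has three possible costs: some avoidable residual variance; an imputation that conditions on less than is known at entry; and no estimate of either primary endpoint by ESA status, so consistency between correction and conversion is not examined directly.

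The dose subgroup does not fill the last gap. As worded it gives no class for untreated subjects or for users of darbepoetin, Mircera or epoetin beta, so it cannot be programmed without a further decision.

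**Working it through.** **1. The plan's own power figure.** SAP 1.3: "With at least 600 subjects, the study will provide at least 99% power to demonstrate non-inferiority"; "This assumes a difference (roxadustat minus epoetin alfa) of -0.30 g/dL". The margin there is -0.75 g/dL and the SD is 1.25 g/dL. SAP 4.3.2 requires that the "lower bound of the 2-sided 95% confidence interval of the difference between roxadustat and epoetin alfa exceeds -0.75 g/dL".

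- Distance from assumed difference to margin: 0.75 - 0.30 = 0.45 g/dL.
- SE with 300 per arm: 1.25 × √(2/300) = 0.102.
- Power: Φ(0.45/0.102 - 1.96) = Φ(2.45) = 99.3%.

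The stated figure reproduces without an ESA term. At about 2000 subjects, power exceeds 99.99%.

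**2. Precision gained by adding the term.** The documents give neither the untreated share p nor the Hb gap g between ESA groups at equal baseline Hb. Assumptions: p = 10-30%; g = 0.2-0.8 g/dL; baseline Hb 10.4 (SD 0.8) if treated and 9.0 (SD 0.7) if untreated; residual SD 1.15 (variance 1.3225).

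Baseline Hb already carries part of ESA status. With V = p(1-p), the baseline variance is (1-p)×0.64 + p×0.49 + V×1.4², and the squared correlation of ESA status with baseline Hb is ρ² = V×1.4² / that variance. The extra variance when ESA is omitted is E = g² × V × (1-ρ²), and the fractional reduction from adding it is E / (1.3225 + E).

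| p | ρ² | V(1-ρ²) | g = 0.2 | g = 0.8 |
|---|---|---|---|---|
| 10% | 0.22 | 0.070 | 0.2% | 3.3% |
| 20% | 0.34 | 0.106 | 0.3% | 4.9% |
| 30% | 0.41 | 0.124 | 0.4% | 5.7% |

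Applying the largest value to the planning SD at 2000 subjects, the 95% CI half-width goes from 1.96 × 1.25 × √(2/1000) = 0.110 to 0.110 × √(1-0.057) = 0.106 g/dL.

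This uses one common baseline-Hb slope and no missing data. It therefore says nothing about an ESA-by-baseline interaction or about the imputation.

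**3. Chance imbalance.** The 95% bound on the shift in the unadjusted arm difference is 1.96 × √(4p(1-p)/N) × g. With wider assumptions (p = 10-50%, g = 0.5-1.0 g/dL), it is 0.013-0.044 g/dL at N = 2000 and 0.024-0.080 at N = 600, against the 0.45 g/dL of room.

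**4. What an ESA subgroup could show.** With n = 1000p untreated subjects per arm and SD 1.25, the half-width is 1.96 × 1.25 × √(2/n). The interaction half-width is 1.96 × 1.25 × √(2/n + 2/(1000-n)).

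| Untreated share (assumed) | n per arm | Half-width, untreated | Interaction half-width | Power for non-inferiority in untreated |
|---|---|---|---|---|
| 10% | 100 | 0.35 | 0.37 | 72% |
| 20% | 200 | 0.25 | 0.27 | 95% |
| 30% | 300 | 0.20 | 0.24 | 99.3% |

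All three untreated half-widths are below 0.45 g/dL, so the estimate would be informative.

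**5. What the planned subgroups already show.** Baseline Hb is the mean of the last three central values (SAP 3.1.1). If two of them are below 10, a mean above 10.5 needs a third value above 3 × 10.5 - 2 × 10 = 11.5. The subgroup above 10.5 g/dL is therefore almost entirely converted subjects. The subgroup at or below 10.5 mixes nearly all untreated subjects with converted subjects whose Hb is low.

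**The case against.** Several stronger readings are tempting, and the documents do not support them.

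- **That the plan ignores prior ESA use altogether.** SAP 3.1.6.1 and 4.3.5.1 isolate ESA-naive or near-naive anemic subjects. Those analyses are exploratory, use time to target and week-24 response rather than either primary endpoint, carry no margin and have no ESA-treated counterpart. They narrow the gap without closing it.
- **That consistency cannot be examined at all.** The subgroup above 10.5 g/dL covers conversion well. What is missing is an untreated-only estimate.
- **That the primary comparison is biased or the common slope invalid.** Arms are randomized; omitting a prognostic covariate does not bias the contrast, and the baseline slope need not be correct for it to be valid. Nothing here establishes the need for an interaction term.
- **That users of other analogues drop out of the dose subgroup.** SAP 4.3.7 gives no rule either way.

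It can also be said that imputation runs by arm and conditions on Hb at earlier weeks, which may carry much of what ESA status would add. That is fair, and the effect on the imputation is not quantified here.

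The last argument is that the covariates are deliberately shared with the other program studies. It is weaker, because SAP 1.2.3 already adds dialysis duration to that set. Nor does dialysis duration stand in for ESA status: the protocol's version 7.0 rationale notes that incident patients are often on ESA therapy.

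**Conclusion.** The point holds in limited form. ESA treatment at entry shapes eligibility and starting dose in both arms, yet it enters no confirmatory or sensitivity Hb model, no imputation model and no subgroup of the two primary Hb endpoints.

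Non-inferiority on the US primary endpoint is not threatened: power reproduces at 99.3%, and the plausible chance shift at 2000 subjects is at most about 0.04 g/dL. The precision gain is small, 0.2-6% of residual variance. The main value is a direct estimate of the primary endpoints in untreated and converted subjects, which the trial could deliver with useful precision if roughly 10-30% are untreated. The untreated share, the Hb gap and the baseline distributions are assumptions.

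This is a cheap improvement, not a flaw in the primary analysis.

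**What to change.** Amend the SAP before database lock, in this order:

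1. In 4.3.7, add ESA treatment at entry (yes/no, by the inclusion criterion 4 definition) as a subgroup for both primary Hb endpoints. Note that this definition looks back 4 or 8 weeks from visit 1, whereas 3.1.6.1 and 4.3.5.1 look back 4 weeks from randomization, so the two sets will not coincide exactly.
2. Add the same factor as a main effect to the imputation model (4.2.6) and to the ANCOVA and MMRM Hb models. An interaction with baseline Hb is not required.
3. Replace the epoetin alfa dose subgroup by three classes: no ESA, at most 12,500, and more than 12,500 IU/week in epoetin equivalents. For analysis classification only, count epoetin beta 1:1 with epoetin alfa (they share a column in Protocol Table 4), use the darbepoetin factor of 200 from Table 7, and pre-specify a single Mircera factor within Table 7's 70-80 range, since the range alone does not give a unique class.

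Eligibility already requires ESA status to be known at screening, so no new data collection is needed. The cost is SAP wording, some programming, and one covariate beyond the set shared with the other program studies.

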4.3.3 Primary efficacy endpoint analysis for EU (First Secondary endpoint for FDA)

Mean change in Hb from baseline to the subjects mean level from week 28 to week 36, without having received rescue therapy within 6 weeks prior to and during this 8-week evaluation period and will be analysed using MMRM. The model will contain terms for the baseline Hb measurement, treatment arm, visit, visit by treatment, CV history, geographic region and dialysis duration. Data up to visit of Week 52 will be included in the model.

Non-inferiority of roxadustat compared to epoetin alfa will be declared, and this test is successful, if the lower bound of the 2-sided 95% confidence interval of the difference between roxadustat and epoetin alfa exceeds -0.75 g/dL. The PPS will be used for non-inferiority. In addition to the comparison based on the PPS population, to address the formal test for non-inferiority, results will also be provided based on the FAS population, to allow also for a potential superiority comparison. The latter test is not part of the formal testing sequence.

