8.6.3 Analysis of the primary efficacy endpoint for EU (Secondary Endpoint for FDA)

The primary efficacy endpoint for EU is Hb change from baseline (BL) to the average Hb of weeks 28 to 36, without having received rescue therapy (i.e. RBC transfusion for all subjects and ESA for roxadustat subjects) within 6 weeks prior to and during this 8-week evaluation period and will be analysed using MMRM. The model will contain terms for the baseline Hb measurement, treatment arm, visit, visit by treatment, CV history, geographic region and dialysis duration. Data up to visit of Week 52 will be included in the model. Non-inferiority of roxadustat compared to epoetin alfa will be declared, and this test as successful, if the lower bound of the 2-sided 95% confidence interval of the difference between roxadustat and epoetin alfa exceeds -0.75 g/dL. The PPS will be used for non-inferiority. In addition to the comparison based on the PPS population, to address the formal test for non-inferiority, results will also be provided based on the FAS population, to allow also for a potential superiority comparison. The latter test is not part of the formal testing sequence.

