1.2.2 Scheduled visits during treatment

During the treatment period, subjects will be contacted by telephone at week 1, and will attend study visits every two weeks from weeks 2 to 20. After week 20, study visits will occur every four weeks until the end of treatment period. A study end date will be defined based on when the planned number of events are estimated to be accrued; the EOT visit will occur as soon as possible after that date. An EOS visit will be performed 4 weeks after the EOT.

Figure 1 Study Flowchart

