2.1.2 Per Protocol Set (PPS)

All randomized subjects without important protocol deviations and who have received at least 8 weeks of study treatment and who have valid corresponding Hb measurements will be included in the PPS. A valid corresponding Hb is defined as an Hb value from the central laboratory that is measured at least 2 weeks after the first dose and was either before the last study drug intake or at maximum three days after the last drug intake. Subjects will be analysed according to their randomized study medication irrespective of intake of study medication. Subjects with an important protocol deviation will be included in the PPS up to the time point when the violation was met. For criteria for PPS exclusion, see Table 1 in Section 2.2. Further details of important protocol deviations are available in a Protocol Deviation Plan. Subjects will be censored at the earliest of date of violating an important protocol deviation, the EOS visit, or at last intake of study drug.

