4.3.6 Sensitivity analysis of efficacy endpoints

- The analysis of the primary efficacy endpoint for US will be repeated but will exclude Hb values 6 weeks after the use of rescue therapy. ITT analysis set will be used.
- The analyses of primary efficacy endpoint and the secondary efficacy endpoints will be repeated using the OT+7.
- The analysis of the US primary efficacy endpoint and the Hb related secondary efficacy endpoints will be repeated using the PPS.
- The secondary endpoint of RBC transfusion as rescue therapy will be repeated using the ITT analysis set.
- Change in Hb from baseline using MMRM. Mean change from baseline across all Hb values from week 28 to week 52 will be analysed using baseline Hb as a covariate and treatment group, visit, visit by treatment interaction, CV history, geographic region and dialysis duration as fixed effects. ITT analysis set will be used.

- Proportion of total time of interpolated Hb within the interval of 10-12 g/dL from week 28 to the EOT visit. The difference between roxadustat and epoetin alfa will be compared using an ANCOVA model with baseline Hb as a covariate, and CV history, geographic region and dialysis duration, as fixed effects. ITT analysis set will be used.
- Change in Hb from baseline using PMM – Last Mean Carried Forward, as specified in Section 4.2.8.1. ITT analysis set will be used.
- Change in Hb from baseline using PMM – PMM – Baseline Mean Carried Forward (ANCOVA), as specified in Section 4.2.8.2. ITT analysis set will be used.
- Change in Hb from baseline using PMM – Baseline Mean Carried Forward for roxadustat subjects, MAR assumption for epoetin alfa group (ANCOVA), as specified in Section 4.2.8.2. ITT analysis set will be used.

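### The MMRM for the EU primary endpoint (first FDA secondary) holds the baseline-Hb slope equal at every visit up to week 52; adding a baseline-by-visit term would improve the estimate at no data cost (minor)

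*SAP*

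**What the plan says.** SAP 4.3.3 gives the fixed effects of the MMRM: "The model will contain terms for the baseline Hb measurement, treatment arm, visit, visit by treatment, CV history, geographic region and dialysis duration". Protocol 8.6.3 has the same list and adds "Data up to visit of Week 52 will be included in the model". The general MMRM text in SAP 4.2.7 is permissive ("The MMRM can contain terms for baseline measurement, treatment arm, visit, treatment by visit interaction, and the stratification variables") and leaves details to each endpoint, so it does not supply the missing interaction. On covariance it says that "the unstructured covariance pattern model will be selected first", followed by a fallback sequence that includes compound symmetry. "The PPS will be used for non-inferiority"; the same model is also reported in the FAS for a possible superiority comparison outside the formal sequence.

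The first visit in the model is not stated. Week 2 is an inference. A valid PPS value is "an Hb value from the central laboratory that is measured at least 2 weeks after the first dose" (SAP 2.1.2), and subjects "will attend study visits every two weeks from weeks 2 to 20" (SAP 1.2.2), then every four weeks.

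**The concern.** With a single baseline term, the model assumes that a 1 g/dL difference in baseline Hb carries the same expected difference in outcome at week 2 as at week 36. The treatment rules make that unlikely. The roxadustat dose is held for the first four weeks unless excessive erythropoiesis calls for a reduction, and is then adjusted every four weeks toward 11±1 g/dL (Protocol 7.2.3.3). Epoetin alfa is adjusted to the same range (Protocol 1.2.2). Titration to a common target tends to erase baseline differences, so the influence of baseline on Hb should fade over time.

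Ten of the 18 visits from week 2 to week 52 fall by week 20. The fitted slope is then a compromise between early and late visits and adjusts weeks 28-36 too strongly for baseline. Two things are at stake: the width of the interval and, if data loss depends on baseline Hb differently by arm, the position of the estimate. The analysis is the EU primary test and the first step of the FDA secondary sequence.

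**Working it through.** **1. The plan's own figure.** SAP 1.3 states at least 99% power with 600 subjects for a true difference of -0.30, margin -0.75 and SD 1.25 g/dL. It refers to the week 28-52 endpoint; no power is stated for weeks 28-36, so it serves as the nearest benchmark.

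SE = 1.25 × √(2/300) = 0.102. Power = Φ(0.45/0.102 - 1.96) = 99.3%. The figure reproduces.

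**2. Number of visits.** Weeks 2 to 20 by 2 gives 10; weeks 24 to 52 by 4 gives 8. The total is 18 if the model starts at week 2. A visit-specific slope needs 17 more parameters.

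**3. Precision with complete data.** Let g be the true visit slopes of change on baseline, S the residual covariance and L the week 28-36 average. With unstructured covariance the common slope tends to b = (1'S⁻¹g)/(1'S⁻¹1). The variance of the difference grows from L'SL to L'SL + (L'g - b)² × Var(baseline), so

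SE ratio = √(1 + (L'g - b)² × Var(baseline) / L'SL).

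Assumptions not in the documents: baseline SD 0.6-1.2 g/dL; slope of change moving from near 0 to -0.6 or -0.9 with a time constant of 4 or 10 weeks; residual SD about 1.1 at plateau; three correlation shapes. Results:

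- two serially correlated shapes: ratio 1.004-1.10
- compound symmetry: ratio 1.015-1.30

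Approximate illustrations, using slopes from the fits in step 5 and 1.1² = 1.21 for L'SL:

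- serial, baseline SD 0.9, late slope -0.90 against common -0.61: √(1 + 0.29² × 0.81/1.21) = 1.03
- serial, baseline SD 0.9, -0.87 against -0.43: √(1 + 0.44² × 0.81/1.21) = 1.06
- serial, baseline SD 1.2, -0.86 against -0.42: √(1 + 0.44² × 1.44/1.21) = 1.11
- compound symmetry, baseline SD 0.9, -0.86 against -0.25: √(1 + 0.61² × 0.81/1.21) = 1.12

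**4. Effect on power** (SD 1.25 taken as the case with the interaction):

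| SE ratio | 300 per arm | 1000 per arm |
|---|---|---|
| 1.00 | 99.3% | >99.99% |
| 1.03 | 99.0% | >99.99% |
| 1.10 | 98.0% | >99.99% |
| 1.30 | 92.4% | >99.99% |

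**5. Bias with dropout.** 60,000 simulated subjects, true difference 0, plateau slope -0.9, monotone dropout with an odds ratio of about 2 per baseline SD where it depends on baseline, and 24-28% missing at week 36. Simulation SE is about 0.008 g/dL.

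| Dropout depends on baseline | Absolute bias, common slope | Absolute bias, baseline-by-visit |
|---|---|---|
| equally in both arms | at most 0.009 | at most 0.010 |
| in one arm only | 0.04-0.08 | at most 0.007 |
| in opposite directions | 0.07-0.16 | at most 0.005 |

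In these runs the arm that lost more of its high-baseline subjects had its late mean overstated. The mirror pattern reverses the sign, so the bias can favour either arm.

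**6. Size against the interval and the decision.** At 1000 per arm the SE is 1.25 × √(2/1000) = 0.056. A bias of 0.04-0.08 is 0.7-1.4 SE, and nominal 95% coverage would fall to about 89-70%. Combining an SE ratio of 1.30 with an adverse bias of 0.08: SE = 0.0727 and power = Φ(0.37/0.0727 - 1.96) = 99.9%. With 0.16 instead, the extreme of the opposite-direction runs, power = Φ(0.29/0.0727 - 1.96) = 97.9%.

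**The case against.** The strongest reply is that the documents give none of the quantities behind these sizes: no slopes by visit, no baseline SD, no correlations and no dropout rates. That stands. The titration rules make a fading slope plausible but do not quantify it, and the larger SE ratios need compound symmetry, a late fallback.

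A reader might infer that the test itself is invalid. The documents do not support that. Under unstructured covariance the misfit is absorbed into the residual variance, so the reported SE reflects it; with complete data the randomized difference is unbiased.

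A reader might also infer that any baseline-related dropout biases the result. It does not: equal dependence in both arms gave nothing beyond simulation error. A difference between arms is possible here. The trial is open-label, PPS data stop at last drug intake or a deviation (SAP 2.1.2), and the need for more than one ESA rescue cycle is a listed reason for permanent discontinuation in roxadustat patients (Protocol 3.9.2). Possible is not shown.

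Other analyses help in part. The US primary analysis imputes week by week with baseline Hb in each regression and then fits an ANCOVA to the week 28-52 average (SAP 4.2.6), so it is free of the constraint, and SAP 4.3.6 repeats it in the PPS. It covers a different window, so it is a check and not a replacement. The FAS and OT+7 repeats state no change of covariate terms and would not reveal the problem.

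Finally, the sensitivity MMRM in SAP 4.3.6 might seem to share the defect. Its text reads "Mean change from baseline across all Hb values from week 28 to week 52 will be analysed using baseline Hb as a covariate" and does not say that earlier visits enter. If only weeks 28-52 are modelled, no early visits pull the slope.

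**Conclusion.** The point holds as a minor one. The listed model does force an equal baseline slope across visits, and titration makes that assumption doubtful. The likely cost is a modest loss of precision, roughly 0.4-10% in the SE under serially correlated errors and more under compound symmetry. There is also a conditional bias of about 0.04-0.08 g/dL if strong baseline-dependent dropout occurs in one arm only, with its sign set by the dropout pattern. All these sizes rest on the assumptions in the working, and the week 2 start is inferred.

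It would be tempting to call this a threat to the EU primary test and to the FDA sequence behind it. The plan's own inputs do not bear that out. A bias of 0.08 is about a tenth of the 0.75 g/dL margin, and at 1000 per arm power stays at about 99.9% even with that bias and the largest SE ratio. The PPS size is not stated, so this reassurance assumes that most randomized subjects remain in it. What is affected is the accuracy of the estimate and its interval. This matters most for the FAS superiority comparison, which has no margin to absorb a shift.

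**What to change.** Add a baseline Hb-by-visit interaction to the MMRM in SAP 4.3.3 and Protocol 8.6.3, state the first visit that enters the model, and estimate the week 28-36 contrast at mean baseline Hb. State in SAP 4.3.6 which visits the sensitivity MMRM uses, and add the term there only if visits before week 28 are included.

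The cost is one model term (17 parameters for 18 visits) and a short text change in two documents. No extra data are needed.
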